NICHD	National Institute of Child Health and Human Development

[figure not shown]
[figure not shown]
NICU	Neonatal Intensive Care Unit
NIH	National Institutes of Health
NIPPV	Nasal Intermittent Positive Pressure Ventilation
PAH	Pulmonary Arterial Hypertension
PH	Pulmonary Hypertension
PI	Principal Investigator
PK	Pharmacokinetics
PMA	Postmenstrual Age (gestational age plus postnatal age)
PP	Per Protocol
PTN	Pediatric Trials Network
q	Every
ROP	Retinopathy of Prematurity
SAE	Serious Adverse Event/Serious Adverse Experience
SAR	Suspected Adverse Reaction
U/L	Units per Liter
US	United States

PROTOCOL SUMMARY

Title:	Safety of Sildenafil in Premature Infants with Severe Bronchopulmonary Dysplasia																															
Précis:	This is a multicenter, randomized, placebo-controlled, sequential dose-escalating, double-masked, safety study of sildenafil in premature infants with severe bronchopulmonary dysplasia (BPD).																															
Number of Participants (N) and Dosing Scheme																																

Cohort¹	Treatment Group	Sildenafil Dosing² (mg/kg q 8 hours)	Total (N)	

Placebo (N)	Sildenafil (N)	IV	Enteral	

1	10	30	0.5	1	40	

2	10	30	1	2	40	

3	10	30	2	4	40	

					Cohort¹	Treatment Group		Sildenafil Dosing² (mg/kg q 8 hours)		Total (N)	Placebo (N)	Sildenafil (N)	IV	Enteral	1	10	30	0.5	1	40	2	10	30	1	2	40	3	10	30	2	4	40
Cohort¹	Treatment Group		Sildenafil Dosing² (mg/kg q 8 hours)			Total (N)																										
	Placebo (N)	Sildenafil (N)	IV	Enteral																												
1	10	30	0.5	1	40																											
2	10	30	1	2	40																											
3	10	30	2	4	40																											
Abbreviations: IV, intravenous; N, number of participants; q, every																																
1 Participants will be enrolled into cohorts sequentially (i.e., Cohort 1 then Cohort 2 then Cohort 3) based on safety.																																
2 Route of administration should be via IV route if patient has an IV and IV administration is feasible. However, route of administration, IV or enteral, is left to investigator discretion.																																
Objectives:	
Primary: Describe the safety of sildenafil as determined by incidence of hypotension in premature infants with severe BPD.
 
Secondary: Pharmacokinetics (PK) and preliminary effectiveness of sildenafil for the prevention of pulmonary hypertension in premature infants with severe BPD.
																															

Population:	
Premature infants with severe BPD (inpatient in neonatal intensive care units) will be randomized in a dose escalating approach 3:1 (sildenafil: placebo) sequentially, into each of 3 cohorts. There will be approximately 40 randomized and dosed participants in each cohort for a total of up to 120 participants.
 
For the purposes of this study, severe BPD is defined as:
 
• 32-44 weeks postmenstrual age at enrollment; and• Receiving respiratory support at enrollment
◦ If 32 0/7–35 6/7 weeks postmenstrual age: mechanical ventilation (high frequency or conventional)◦ If 36 0/7–44 6/7 weeks postmenstrual age: mechanical ventilation (high frequency or conventional) OR continuous positive airway pressure (CPAP). 
Note: Exclusion from participation due to enrollment in other clinical trials, including IND trials, will be left to the judgement of the site principal investigator (PI). Investigator judgement should consider the safety of the participant.

Phase or Stage:	2
Number of Sites:	Approximately 30 sites
Description of Intervention:	Sildenafil citrate injection and powder for suspension
Study Duration:	Approximately 36 months enrollment period with an additional 24 months of data analyses (60 months total)
Subject Participation Duration:	Up to 62 days (up to 34 days of study drug plus 28 days of safety monitoring). Information about hospitalization will be collected at 36 weeks postmenstrual age and/or at discharge.

2 INTRODUCTION: BACKGROUND INFORMATION AND SCIENTIFIC RATIONALE

2.1 Background Information

Sildenafil is approved by the FDA for the treatment of pulmonary arterial hypertension in adults to improve exercise ability and delay clinical worsening.¹ The FDA does not recommend using sildenafil for pulmonary hypertension in children 1 to 17 years of age. Recommendations about sildenafil use in neonates and infants do not exist. Differences

[figure not shown]
in the cardiopulmonary pathophysiology targeted to neonates and infants suggest that sildenafil may be beneficial in this population. As a result, pharmacokinetic (PK) and safety studies of sildenafil in neonates and infants have been or are currently being conducted under the Best Pharmaceuticals in Children's Act by the National Institute of Child Health and Human Development (NICHD)-funded Pediatric Trials Network (PTN).² The present study, supported by the National Heart Lung and Blood Institute (NHLBI), will generate additional safety, PK, and preliminary effectiveness data on sildenafil in a subpopulation of infants with severe bronchopulmonary dysplasia (BPD).

2.2 Rationale

Over 50,000 infants are born < 29 weeks gestational age each year in the US, of whom nearly 40% develop BPD.³ BPD is defined by the NIH as either mild, moderate, or severe based on the respiratory support required at 36 weeks postmenstrual age.⁴ Premature infants with severe BPD are particularly challenging and suffer from multiple morbidities including pulmonary hypertension (PH), prolonged hospitalization, death, and life-long morbidities.⁵⁻⁷ Because of the prevalence and seriousness of the disease, neonatologists are dedicated to preventing BPD.⁸ Vitamin A, caffeine, and postnatal steroids have all been shown to prevent BPD.⁹⁻¹¹ Members of this protocol team (Drs. [name], [name], and [name]) are currently performing trials to prevent BPD using sildenafil (NCT03142568). However, once BPD has developed, there are no drugs to prevent its associated morbidities including PH. This study seeks to address this knowledge gap by evaluating the safety, PK, and preliminary effectiveness of sildenafil in this population and was designed based on the rationale outlined below.

Pulmonary hypertension is a deadly complication of severe BPD. Approximately 20% of premature infants with severe BPD develop PH, and up to 40% of premature infants with severe BPD and PH die, usually due to right heart failure.^{5,12,13} In addition to higher mortality, infants with combined BPD and PH have longer hospitalizations and are more likely to require in-home respiratory support.^{14,15} The temporal relationship between BPD and PH in premature infants is complex. Early PH without concurrent BPD can be present in the first week of life in infants at the highest risk of BPD, such as those with fetal growth restriction.¹² Only one-third of these infants will develop BPD later in life. In contrast, most infants with BPD who develop PH do so later in life: one prospective study of extremely low-birth-weight infants found that 65% of infants with BPD-related PH had normal echocardiograms at 4-6 weeks.¹⁶ BPD-related PH occurs due to impaired lung development resulting in decreased pulmonary vessel branching and vascular remodeling (Figure 1).¹⁷ Knowledge of this pathology and the delay in development of this severe complication offer an opportunity for prevention to decrease infant mortality.

Figure 1 Pathophysiology of pulmonary hypertension in infants with BPD

Abbreviations: BPD, bronchopulmonary dysplasia; PH, pulmonary hypertension

Sildenafil reduces lung injury and preserves normal vasculature in preclinical BPD models. BPD and PH are characterized by lung injury, inflammation, abnormal alveolarization, and dysregulated vascular development. Preclinical models demonstrate that sildenafil might prevent ischemic-perfusion injury and improve lung function (rat¹⁸), suppress inflammatory mediators (mouse¹⁹; rat^{20,21}; also matrix metalloproteinase-2 in cell cultures²²) that contribute to lung injury and BPD, and improve alveolarization and lung vascular development. Sildenafil is a potent inhibitor of phosphodiesterase type 5, the predominant isoform in the lung, which metabolizes cyclic guanosine monophosphate and produces pulmonary vasodilation. Sildenafil may thus prevent the development of BPD-related PH in premature infants by reducing pulmonary vascular remodeling and lowering pulmonary vascular resistance, but clinical trial evidence is needed.

Sildenafil improves short-term outcomes in children and adults with pulmonary hypertension. Sildenafil is a potent inhibitor of type 5 phosphodiesterase, the

predominant isoform in the lung. Type 5 phosphodiesterase metabolizes cyclic guanosine monophosphate and produces pulmonary vasodilation. In adults, sildenafil is approved by the FDA for the treatment of pulmonary arterial hypertension.¹ Children with pulmonary arterial hypertension (either idiopathic or due to preexisting cardiac disease) treated with sildenafil had improved aerobic capacity after 16 weeks of treatment, and the effect appeared to be dose dependent.^{23,24} In this study, children with BPD were excluded, and all participants were > 8 kg. Long-term follow-up demonstrated an increased risk of mortality in the highest sildenafil dosing group, (dosing was weight-based with the highest dose group receiving 20 mg thrice daily if weight was 8-20 kg, 40 mg thrice daily if weight was 21-45 kg and 80 mg thrice daily if weight was > 45 kg).²⁵ FDA does not recommend sildenafil use, particularly chronic use, in children and Health Canada states sildenafil is not indicated in pediatric patients.^{1,26}

Neonatologists frequently use sildenafil to treat infants with pulmonary hypertension. Two case reports documented the successful resolution of PH, measured by echocardiogram, in premature infants treated with sildenafil.^{27,28} In a small case series, enteral sildenafil at a dose range of 1.5-8 mg/kg/day in 25 premature infants with a median gestational age of 28 weeks (range 23-41 weeks) with lung disease (72% with BPD) resulted in improved hemodynamics by echocardiogram.²⁹ A retrospective case series of 23 preterm infants with median gestational age of 26 weeks treated with 1-7.3 mg/kg/day of oral sildenafil found a substantial improvement in BPD related PH based on echocardiography in 71% of patients for whom echocardiographic data were complete (15/21).³⁰ These data confirm that neonatologists usually treat PH in infants with BPD and are likely unwilling to randomize to placebo; thus, a prevention approach is needed.

Neonatologists are using sildenafil without safety data. Neonatologists are increasingly using sildenafil in premature infants despite a lack of sufficient safety data, including data related to hypotension and retinopathy of prematurity (ROP). Despite neonatal medicine's long history of catastrophic adverse events (AEs) resulting from inadequate study of drugs prior to their widespread use,³¹⁻³⁴ the majority of drugs used in premature infants, including sildenafil, have undergone insufficient study to receive FDA labeling for this population.³⁵⁻³⁹ Extrapolating drug safety and dosing from adults underestimates the complicated physiology of premature infants, who have (1) larger extracellular fluid volume per unit body weight, (2) immature renal and hepatic function, and (3) disease-related changes in metabolizing organ function, each of which can alter drug disposition.^{40,41} Improper use of drugs in these vulnerable patients leads to increased treatment failure, AEs, mortality, and long-term morbidities.⁴² Sildenafil studies specifically designed for premature infants with BPD are urgently needed. These studies should initially focus on characterizing PK and safety in infants to inform the design of a pivotal efficacy trial.

Sildenafil is increasingly used off-label in premature infants with BPD: A review of data from the Mednax Clinical Data Warehouse, a real-world data source representing approximately 20% of US Neonatal Intensive Care Unit (NICU) admissions,⁴³ found an

exponential increase in sildenafil use by > 1000%, second highest of all drugs from 2005 to 2010.⁴⁴ Of the infants exposed to sildenafil, 79% had BPD and 84% had PH.

A phase 1 opportunistic pilot study of sildenafil in premature infants under IND (NCT01670136) has been completed. Conducted under IND by the PTN, the trial enrolled 34 infants ≤ 28 weeks gestational age with a median birth weight of 666 g receiving intravenous (IV) or enteral sildenafil per standard of care at doses between 0.13 mg/kg - 2.1 mg/kg. Pharmacokinetic and safety analyses were performed and are summarized below.

The infant population PK model identified safe sildenafil starting doses for early phase trials. Using 109 plasma samples collected in 34 infants in a multicenter phase 1 open-label PK study of sildenafil in premature infants, we developed a 2-compartment population PK model of sildenafil and its primary active metabolite N-desmethylsildenafil (DMS). Population estimates of parent sildenafil elimination clearance and central volume of distribution were 27.8 L/h/70kg and 116 L/70kg; relative DMS elimination clearance and volume of distribution, were 135 L/h/70kg and 1670 L/70kg.² The model simulated sildenafil and DMS exposures at different enteral and IV dosing regimens to identify safe doses for evaluation in a dose escalation trial (Table 1). Starting doses of 0.5 mg/kg IV (or 1 mg/kg enteral) resulted in combined AUC_{0-24,SIL+DMS} comparable to a previously reported value of 2650 ng*hr/mL which has been associated with infant survival.⁴⁵ However, exposure targets for PH prevention in infants with severe BPD are unknown and will be further elucidated in this trial.

Table 1 Simulated Median Steady-State Area under the Concentration vs. Time Profile 0- 24 Hours

Intravenous Dosing (every 8 hours)	0.5 mg/kg	1 mg/kg
Sildenafil (ng*hr/ml)	3157	6314
DMS (ng*hr/ml)	669	1337
Sildenafil + 62.5%DMS (ng*hr/ml)	3581	7163
Enteral Dosing (every 8 hours)	1 mg/kg	2 mg/kg
Sildenafil (ng*hr/ml)	1825	3650
DMS (ng*hr/ml)	1608	3217
Sildenafil + 62.5%DMS (ng*hr/ml)	2941	5883

Abbreviation: DMS, N-desmethylsildenafil

The safety analysis identified overall incidence and events of special interest: The safety analysis included all 34 infants. There were 23 adverse events in 15 participants and 5 serious adverse events (SAEs) in 5 participants, including 1 episode of hypotension, the only event related to sildenafil, in an infant receiving IV sildenafil (Table 2). This event was determined to be related to a faster than expected infusion rate of IV sildenafil. The event led to a data monitoring committee (DSMB) review of available data, and a review of all clinical sites' infusion methods and equipment. The protocol was changed prior to enrolling the remaining Cohort 2 subjects to include a

longer infusion time (30 minutes) and the dose was lowered by 50% to 0.125 mg/kg. When the study reopened, 2 additional subjects were enrolled without any related AEs.

Table 2 Summary of All Adverse Events in Phase 1 Study of Sildenafil

	Cohort 1 (N = 25)	Cohort 2 (N = 9)
Number of Events/Participants		
Number of AEs	13	10
Participants with at least one AE	8 (32.0%)	7 (77.8%)
Number of SAEs	1	4
Participants with at least one SAE	1 (4.0%)	4 (44.4%)
Severity (All AEs)		
Mild	7	3
Moderate	4	3
Severe	2	4
Highest Severity per Participant		
Mild	4 (16.0%)	2 (22.2%)
Moderate	3 (12.0%)	1 (11.1%)
Severe	1 (4.0%)	4 (44.4%)
Relationship (All AEs)		
Not related	13	9
Related	0	1
Strongest Relationship per Participant		
Not related	8 (32.0%)	6 (66.7%)
Related	0	1 (11.1%)

Abbreviations: AE, adverse event; N, number of participants; SAE, serious adverse event

Echocardiography is a reliable surrogate endpoint for the diagnosis of pulmonary hypertension in premature infants: With support from NHLBI (R34HL14038), members of the current study team (Drs. [name] and [name]) assigned 3 blinded pediatric cardiologists to review 483 echocardiograms from 49 infants < 29 weeks gestational age at birth (range 22–28) admitted to the neonatal intensive care units of UNC or Duke. PH diagnosis was a priori defined using tricuspid regurgitation jet and, if unavailable, a composite score of echocardiographic measures. The proposed score had high inter (modified Fleiss Kappa 0.759 (0.771, 0.801) and intra-rater reliability (Fleiss Kappa 0.847 (0.75, 0.931), and acceptable internal consistency (Cronbach's alpha 0.64)⁴⁶. Importantly, the score identified infants with PH with a prevalence (33%) and mortality (34%) comparable to prior reports. Mortality was significantly lower (10%) for infants not diagnosed with PH.

Based on the above data, sildenafil is a promising potential intervention to prevent the development of PH in premature infants with BPD. Prior to the completion of definitive efficacy trials, an evaluation of its safety, PK, and preliminary effectiveness are essential.

2.3 Potential Risks and Benefits

2.3.1 *Potential Risks*

2.3.1.1 Risks of Blood Sampling

There are small risks to blood sampling including minor pain or discomfort with the needle stick and blood loss. Every effort will be made to avoid needle sticks in excess of standard of care for this study and every effort will be made to time clinical blood draws to coincide with timed samples, using existing IV lines when possible.

2.3.1.2 Sildenafil

There are several risks associated with administering sildenafil in premature infants, including:

1. A theoretical increased risk of ROP associated with sildenafil has been suggested in a case report in the literature;⁴⁷ however, case-control and cohort studies have not found a significant association between sildenafil exposure and ROP.^{48–50}
2. Sildenafil has vasodilatory properties that can result in mild and transient decreases in blood pressure. See sildenafil package insert for additional information.¹

Adverse events were previously observed in the phase 1 opportunistic pilot study of sildenafil in premature infants (NICHD-2012-SIL0; see Table 2, Section 2.2). Safety data will also be reviewed prior to dose escalation between cohorts. Risks of ROP have been minimized by administering sildenafil during the time when screening for ROP begins (31-32 weeks adjusted age). Treatment of ROP is an exploratory outcome (Section 3.3.1).

2.3.2 *Potential Benefits*

Sildenafil may improve pulmonary mechanics, reduce exposure to mechanical ventilation, and prevent PH. Although these improvements are not proven, improved pulmonary function and decreased risk of PH are potential benefits for participants enrolled in the study who receive sildenafil. Conclusions drawn from this study will benefit infants receiving sildenafil in the future through better understanding of dose response and characterization of the safety profile of sildenafil.

3 OBJECTIVES AND OUTCOME MEASURES

3.1 Objectives

3.1.1 *Primary Objective*

Describe the safety of sildenafil in premature infants with severe BPD.

3.1.2 Secondary Objectives

Analyze the pharmacokinetics (PK) and preliminary effectiveness of sildenafil in premature infants with severe BPD.

3.1.3 Tertiary/Exploratory Objectives

Explore other events of interest in premature infants with severe BPD.

3.2 Outcome Measures

3.2.1 Primary Outcome Measures

Safety as determined by incidence of hypotension experienced by the participants through 28 days post last dose of study drug.

Hypotension will be defined as any clinically significant low blood pressure event deemed by the treating physician to require intervention with a fluid bolus or the initiation or escalation of inotropic, vasopressor, or systemic steroid therapy with the specific intent to raise blood pressure.

3.2.2 Secondary Outcome Measures

3.2.2.1 Pharmacokinetics

A population PK analysis will be performed. Using the final population PK model, empirical Bayesian estimates of clearance, volume of distribution, and half-life will be generated for each participant and used to calculate exposure metrics (e.g. AUC, maximum concentration).

3.2.2.2 Preliminary Effectiveness

The presence or absence of PH will be determined using central review by blinded pediatric cardiologists of echocardiograms performed at the end of the study period.

The developed population PK model will be linked to the diagnosis of PH made by echocardiography at the end of the study period to develop a population PK/PD model. We will use the model to simulate the effect of variable sildenafil exposures on the probability of developing PH.

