⁸ Dosing may be adjusted according to any weight changes determined at baseline, study Days 7, 14, and 21.

⁹ Concomitant medications of special interest will be recorded during the entire study period.

¹⁰ AEs will be collected following informed consent through 28 days post last dose of study drug.

¹¹ If performed per local standard of care

¹² Transfer, discharge, duration of hospitalization or death; record if treatment for ROP was required.

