8 STUDY PROCEDURES/EVALUATIONS

8.1 Study Procedures/Evaluations

- A focused medical history of the participant will be extracted from the medical record.
- Concomitant medication information including name, route of administration, and dose will be extracted from the medical record.
- Physical examination including the vital signs (MAP) listed under the study schedule will be extracted from the medical record.
- Echocardiogram images will be uploaded for central review and interpretation at the coordinating center.
- Echocardiogram dates and reports will be collected in the EDC.
- Cardiac catheterization dates and reports will be collected in the EDC.
- Biological specimen collection will be performed per local procedures. See the MOP for further detail about biological specimen handling, storage, and shipping.
- Respiratory assessments will be extracted from the medical record (see Section 8.2.2.3 for more details).
- Discharge information will be extracted from the medical record.
- Protocol-specified MAP values will be obtained per local procedures.
- Blood pressure will be determined using MAP. For each participant, MAPs will be taken as noted in Section 4.2. Mean arterial pressure will be measured using an appropriate size cuff or with an intra-arterial placed catheter that measures continuous blood pressure.

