A multivariable mixed-effects model will be used to explore the relationship between the maximum and total dose of sildenafil and change in PH, death, and death or PH at 28 days of study drug and at the end of hospitalization or 52 weeks PMA, whichever comes first. We will use 52 weeks PMA because we found that 95% of infants with severe BPD died or were discharged home by this time.⁷

Planned sensitivity analyses of the primary endpoint

To address the potential effect of multiples enrolled in the study on the primary endpoint, we will conduct the following 2 sensitivity analyses:

- Sensitivity analysis #1 using only the first randomized sibling from any multiple gestations.
- Sensitivity analysis #2 using generalized estimating equations (GEE) with log link random effect for siblings to compute ratios of hypotension between the sildenafil and placebo groups.

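### PH is read at an undefined end-of-study echocardiogram but used to model who develops PH, so PH that clears under treatment counts as absent and earlier deaths have no PK/PD outcome

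*Combined protocol and SAP*

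**What the plan says.** Section 3.2.2.2 settles the presence or absence of PH through a central, blinded cardiology read of "echocardiograms performed at the end of the study period". The population PK model is then "linked to the diagnosis of PH made by echocardiography at the end of the study period", and the result is used to simulate how exposure changes an infant's chance of developing PH. The text supplied does not define that time.

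Section 12.4 uses other times. A mixed-effects model relates maximum and total sildenafil dose to "change in PH, death, and death or PH at 28 days of study drug and at the end of hospitalization or 52 weeks PMA", whichever of the last two is earlier.

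Section 4.4 requires one post-baseline echocardiogram of every infant, on follow-up Day 1 (+2 days), counted from the last dose with weaning doses included. For treatment, weaning and the final assessment, Table 6 marks the echocardiogram with footnote 11: "If performed per local standard of care". Section 8.1 says "Echocardiogram images will be uploaded for central review and interpretation at the coordinating center", without limiting this to any visit.

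On treatment of PH, Section 2.2 states: "These data confirm that neonatologists usually treat PH in infants with BPD". It cites a retrospective series of infants on oral sildenafil that "found a substantial improvement in BPD related PH based on echocardiography in 71% of patients" with complete data (15 of 21). Section 6.5 permits any concomitant treatment. Section 6.5.1 records inhaled nitric oxide, bosentan, epoprostenol, milrinone and sildenafil, along with several diuretics, for the whole study. Of these drugs, Section 5.5.1 names only inhaled nitric oxide as a start that ends study drug. Infants with PH on the qualifying echocardiogram are excluded (Section 5.2), so PH seen later is new.

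**The concern.** The aim is prevention, and the simulation concerns developing PH, which is an incidence question. The measurement is status at one time. The two agree only if PH, once present, is still visible at the read and the infant is alive to be read. The protocol itself describes how the first condition can fail: PH is usually treated, treatment can improve the echocardiogram, and all treatment is allowed. No rule in the text counts earlier PH, or the start of PH therapy, as an event.

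The second condition fails through death. In the study team's echocardiography work cited in Section 2.2, mortality was 34% with PH and 10% without. Infants who die before the read are therefore not a random subset, and the PK/PD link in Section 3.2.2.2 gives them no outcome.

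The PK/PD model is the most exposed. Under Section 8.2.2.3 (Minimizing Blood Loss), placebo infants have biomarkers measured in place of drug levels. If they enter the model at zero exposure, a placebo infant whose PH was cleared by open-label sildenafil appears as no exposure and no PH.

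**Working it through.** **Plan's own figures.** The only design figures concern hypotension, and they reproduce: 1 − 0.95^30 = 0.785 (stated 78%) and 1 − 0.95^90 = 0.990 (stated 99%). No power, effect size or event count is given for PH.

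**Timing.** For infants completing 28 days, the mandatory echocardiogram falls on study Days 29–31 in Cohort 1 (28 + 1, plus up to 2). In Cohorts 2 and 3 it falls on Days 35–37 (28 + 6 weaning days + 1, plus up to 2). For an infant who stops early it follows that infant's last dose. None of these is exactly the 28-day time in Section 12.4. The later Section 12.4 time has no required echocardiogram: the one at discharge or transfer depends on local care (Section 4.5), and Table 6 has no 52-week visit.

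**Inputs for the loss.**
- N = 120, of which 30 are pooled placebo and 90 sildenafil (Sections 4, 5.4.1 and 12.4).
- PH risk p = 20% (Section 2.2), or 33% (prevalence in the echocardiography study, same section).
- t = share of PH cases treated before the read. The documents give no value; 10–50% is assumed.
- r = share of treated cases resolved by the read. The documents give no value; 25% up to 15/21 = 71% is assumed. The 71% is improvement, not resolution, so it serves only as an upper bound.

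**Formulas.** Expected cases = N × p. Fraction lost f = t × r. Cases lost = N × p × f.

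Expected cases: 120 × 0.20 = 24 (6 placebo and 18 sildenafil if there is no effect); 120 × 0.33 = 39.6.

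| t | r | f | Lost of 24 | Lost of 39.6 |
|---|---|---|---|---|
| 10% | 25% | 2.5% | 0.6 | 1.0 |
| 50% | 25% | 12.5% | 3.0 | 5.0 |
| 50% | 50% | 25% | 6.0 | 9.9 |
| 50% | 71% | 35.7% | 8.6 | 14.1 |
| 100% (ceiling) | 71% | 71.4% | 17.1 | 28.3 |

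**Effect on a contrast.** Assume, for illustration, 20% PH on placebo and 10% on sildenafil.
- *Equal loss in both arms.* Risk difference = 10 × (1 − f) points: 9.75 at f = 2.5% and 6.4 at f = 35.7%. Risk ratio = 0.10(1 − f) / 0.20(1 − f) = 0.50 throughout.
- *Loss on placebo only.* Apparent risk ratio = 0.50 / (1 − f): 0.54 at f = 7.1% (t = 10%), 0.61 at 17.9% (t = 25%) and 0.78 at 35.7% (t = 50%), each with r = 71%.

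The placebo-only case is a bound. In a double-masked trial the documents give no reason to expect the loss in one arm alone.

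**The case against.** A reader might infer that PH is judged on one echocardiogram only and that the endpoint loses most of its cases. The documents do not support that, for four reasons.

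- Section 12.4 analyses PH at two times and already includes death and death or PH. The death gap is confined to the PK/PD link.
- The 71% is improvement in 21 infants from a retrospective series. It says nothing of resolution or of time to improvement. To be missed, PH must arise, be found, be treated and normalise within about 28 days, or about 34 with weaning. No share treated in that window is given.
- Starting inhaled nitric oxide ends study drug, and the mandatory echocardiogram follows within days, or after the six-day wean where that applies. Some treated cases will be seen.
- Equal loss costs precision but leaves the risk ratio intact.

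There is also a real case against making PH at any time the main endpoint. Echocardiograms during treatment are ordered locally at about 30 sites, so detection would depend on how often an infant is imaged. The follow-up Day 1 echocardiogram is the only post-baseline one required of everyone.

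All of this stands and limits the point. It does not supply a definition of the read time, a rule for PH treated earlier, or a PK/PD outcome for infants who die first. The separate statistical and PK analysis plans announced in Section 12.4 are not among the documents and may say more.

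**Conclusion.** The point holds as a gap in definition with a partial, unquantified loss of cases. Status at an undefined time stands in for developing PH, treated and cleared PH is scored absent, and deaths before the read drop out of the PK/PD link.

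Under the assumed ranges, the loss runs from negligible to about a third of cases. The 71% ceiling needs every case to be treated and every improved case to count as resolved, which the documents do not support. The number of deaths before the read cannot be derived from the documents.

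The analysis is secondary and exploratory, and the primary hypotension outcome is unaffected. With about 6 expected placebo cases at 20% PH, though, losing one or two would matter to a model meant to inform a later efficacy trial.

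**What to change.** 1. State in Section 3.2.2.2 that the PH read is the mandatory follow-up Day 1 (+2 days) echocardiogram, and keep it as the main read. Reconcile it with the two times in Section 12.4, noting that the later one has an echocardiogram only if local care orders it.
2. Use death or PH as the PK/PD outcome, or at least as a pre-specified co-analysis, so that deaths before the read are not dropped.
3. Add a pre-specified sensitivity analysis that counts an infant as having PH if, by the time point, there is PH on any centrally read post-baseline echocardiogram or on catheterization, or a start of inhaled nitric oxide, bosentan, epoprostenol, milrinone or non-study sildenafil. The diuretics in Section 6.5.1 should not count.

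The cost is analysis-plan wording, some programming and central reading of images that Section 8.1 already has uploaded. No new data are needed. The downside is that local echocardiograms and drug starts are clinically triggered and vary by site. A drug start may also not be for PH, since Section 8.1 mentions drug name, route and dose but not indication. That is why item 3 is a sensitivity analysis and not a replacement endpoint.
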